STUDY PROTOCOL AND STATISTICAL ANALYSIS PLAN (SAP)

Comparison of the Efficacy of Nasal Mask and Nasal Cannula Oxygenation During Gastrointestinal Endoscopic Procedures Performed Under Target-Controlled Propofol Infusion Anesthesia With SedLine Brain Function Monitoring: A Randomized Controlled Trial

Impact of Nasal Mask Versus Nasal Cannula Oxygenation on Hypoxemia in Gastrointestinal Endoscopy: A SedLine-Guided Randomized Controlled Trial

NCT ID: Not yet assigned (pending)

Unique Protocol ID: 2024/392

Secondary ID / Other Identifier: 2024/392

Issuing Organization: SBÜ Sancaktepe Şehit [name]. İlhan Varank Training and Research Hospital Scientific Research Ethics Committee

Facility: University of Health Sciences Sultan Abdulhamid Han Training and Research Hospital, Istanbul, Turkey

Ethics approval: Approval No. 2024/392 (December 26, 2024)

Study Start Date: January 06, 2025 (Actual)

Primary Completion Date: August 26, 2025 (Actual)

Study Completion Date: November 15, 2025 (Actual)

Overall Recruitment Status: Completed

Enrollment: 600 participants (Actual)

Document Date: December 15, 2025

Table of Contents

Note: Update this section after final formatting (Word can auto-generate a TOC).

1. Study Synopsis

Design: Prospective, randomized, parallel-group, open-label controlled trial.

Population: Adults (18–75 years), ASA physical status I–III, scheduled for gastroscopy and colonoscopy in the same session.

Interventions: Oxygen at 4 L/min via a nasal mask versus standard nasal cannula during target-controlled propofol sedation.

Sedation monitoring: SedLine® brain function monitoring with Patient State Index (PSI) targeted between 50 and 80.

Primary outcome: Hypoxemia incidence ($\text{SpO}_2 \leq 90\%$).

Sample size: 600 participants (300 per group).

2. Background and Rationale

Hypoxemia is a common and clinically important adverse event during propofol-sedated gastrointestinal endoscopy. Standard nasal cannula oxygen supplementation may be insufficient in some patients. A nasal mask can improve oxygen delivery and potentially reduce hypoxemia and airway interventions. This trial evaluates whether a nasal mask reduces hypoxemia compared with a standard nasal cannula under a standardized, SedLine-guided, target-controlled infusion (TCI) propofol sedation protocol.

3. Objectives

Primary objective: To compare the incidence of hypoxemia ($\text{SpO}_2 \leq 90\%$) between the nasal mask and nasal cannula groups during the procedure.

Secondary objectives: To compare severe hypoxemia, hypoxemia duration, minimum SpO_2 , need for airway interventions, procedure time, recovery time, adverse events, and clinician satisfaction scores.

4. Study Design

This is a single-center, interventional, randomized (1:1), parallel-assignment trial.

Blinding was not feasible due to the visible oxygen delivery device.

5. Study Population

5.1 Inclusion Criteria

- Age 18–75 years
- ASA physical status I–III
- Scheduled to undergo both gastroscopy and colonoscopy in the same session
- Planned intravenous propofol sedation for the procedure

5.2 Exclusion Criteria

- Myocardial infarction within 6 months or unstable angina history
- Severe arrhythmia history
- Acute pharyngitis, tonsillitis, or pneumonia
- Baseline room air $\text{SpO}_2 \leq 90\%$
- Severe cardiopulmonary disease or anticipated difficult airway
- Severe obstructive sleep apnea syndrome
- Known allergy to propofol, egg, soy, albumin, lidocaine, or similar agents
- Pregnancy or lactation
- Participation in another clinical study within the previous 3 months
- Inability to provide informed consent

6. Randomization and Allocation

Participants were randomized 1:1 to nasal mask versus nasal cannula oxygenation using a pre-prepared randomization list. Allocation was implemented using opaque, sealed envelopes.

7. Interventions and Procedures

7.1 Oxygenation

Nasal mask arm: Oxygen at 4 L/min delivered via a nasal mask covering the nasal area.

Nasal cannula arm: Oxygen at 4 L/min delivered via a standard adult nasal cannula.

7.2 Sedation Protocol

All participants received propofol sedation using a target-controlled infusion system.

Sedation was titrated to maintain SedLine PSI values between 50 and 80. Standard monitoring included noninvasive blood pressure, ECG, heart rate, and peripheral oxygen saturation (SpO_2).

8. Outcome Measures

8.1 Primary Outcome

Incidence of hypoxemia during the procedure, defined as any occurrence of $\text{SpO}_2 \leq 90\%$.

8.2 Secondary Outcomes

- Severe hypoxemia: $\text{SpO}_2 \leq 75\%$ or $\text{SpO}_2 \leq 90\%$ for >60 seconds
- Duration of hypoxemia (seconds)
- Minimum SpO_2 during the procedure
- Need for airway interventions
- Adverse events

- Procedure time and recovery time
- Clinician satisfaction scores (0–100)

9. Statistical Analysis Plan

All analyses were performed in the intention-to-treat population using IBM SPSS Statistics (version 26.0). Sample size calculations were performed using PASS (version 11.0). Two sided $p < 0.05$ was considered statistically significant unless otherwise specified.

Normality was assessed using the Shapiro–Wilk test. Continuous variables were compared using the independent samples t test or Mann–Whitney U test, as appropriate, and are reported as mean \pm standard deviation or median [interquartile range]. Hodges–Lehmann median differences with 95% confidence intervals were calculated for selected non normally distributed continuous outcomes. Categorical variables were compared using chi square or Fisher’s exact tests, and key binary outcomes were reported with relative risk and odds ratio with 95% confidence intervals.

Baseline balance was assessed using absolute standardized difference ($|ASD| < 0.10$). Spearman correlation was used for associations between continuous variables. PSI was defined as the mean between 5 and 20 minutes after induction (PSI 5–20). Exploratory minute based logistic regression at 5, 10, 15, and 20 minutes used Bonferroni correction ($p < 0.0125$). Subgroup analyses (age, sex, BMI, ASA) used treatment-by-subgroup interaction terms (Wald test) with Bonferroni corrected threshold $p < 0.0125$ for interaction testing. Multivariable logistic regression was used to identify predictors of hypoxemia.

10. Ethics and Dissemination

The study was approved by the local ethics committee and conducted in accordance with the Declaration of Helsinki. Written informed consent was obtained from all participants.

11. Version History

Version: 1.0

Date: December 15, 2025

Summary of changes: Initial version prepared for ClinicalTrials.gov PRS Study Documents upload.

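### Clinician satisfaction is compared without regard to which clinician gave the rating: this costs precision, and it overstates certainty only if the result is read as applying to clinicians in general

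*Combined protocol and SAP*

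**What the plan says.** Section 8.2 names the outcome only as "Clinician satisfaction scores (0–100"). It does not say whether the rater is the endoscopist, the sedation provider or both, how many people rate, or how many sessions each rates.

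Section 9 has no rule specific to this score, so the general one applies: "Continuous variables were compared using the independent samples t test or Mann–Whitney U test, as appropriate". An interval is promised in these terms: "Hodges–Lehmann median differences with 95% confidence intervals were calculated for selected non normally distributed continuous outcomes". Whether satisfaction is among the selected outcomes is not stated. The significance rule is "Two sided $p < 0.05$ was considered statistically significant unless otherwise specified". Section 9 contains no clinician term, mixed model or cluster-robust variance.

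Three design facts matter here:

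- Section 4: "This is a single-center, interventional, randomized (1:1), parallel-assignment trial".
- Section 6: "Participants were randomized 1:1 to nasal mask versus nasal cannula oxygenation using a pre-prepared randomization list". No stratification by clinician is mentioned.
- Section 4: "Blinding was not feasible due to the visible oxygen delivery device". Whoever rates can therefore see the device.

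The synopsis gives "Sample size: 600 participants (300 per group").

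**The concern.** The patient is randomized, but a clinician supplies the score. One center treated 600 participants between the study start (January 6, 2025) and primary completion (August 26, 2025). It is hard to see how that could happen without the same clinicians rating repeatedly, and, under individual randomization, rating both devices.

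Two kinds of between-clinician variation then enter the score, with different consequences:

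- **Rating level.** Some clinicians score everything higher than others. The planned tests leave this variation in the error term, although a clinician factor could remove it.
- **Device preference.** Clinicians may differ in how much they like the mask relative to the cannula. This is plausible for a subjective score of a visible device. Its contribution to the uncertainty about an average clinician shrinks with more clinicians, not with more patients per clinician, and the planned tests do not see it.

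At stake are some lost power on this one secondary outcome, and a p-value from 600 patients that may be taken as evidence about clinicians in general, which the plan neither supports nor rules out.

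**Working it through.** **No plan figure to reproduce.** The documents give no SD, target difference or power for satisfaction. They also give no event rates, power or dropout for the total of 600, so that number cannot be reproduced either.

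**Inputs from the documents.** 300 per arm; two-sided 0.05; one center; individual 1:1 randomization; 232 days from start to primary completion, so 600 / 232 ≈ 2.6 sessions per calendar day.

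**Inputs that are assumptions.** Residual SD 15; between-rater SD 8; SD of the rater-specific device effect (τ) 0, 3 or 5 points; number of raters K = 4, 6, 10 or 20.

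**Step 1: raters differ only in level (τ = 0).**

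- Planned SE = √[(2/300) × (15² + 8²)] = √1.927 ≈ 1.39.
- SE with clinician as a factor and arms nearly balanced within clinician ≈ √[(2/300) × 15²] = √1.5 ≈ 1.22.
- Power for a true 3.5-point difference, planned: Φ(3.5/1.388 − 1.96) = Φ(0.56) ≈ 71%.
- Power with clinician in the model: Φ(3.5/1.225 − 1.96) = Φ(0.90) ≈ 82%.

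Validity was checked by simulation with unstratified individual randomization. Using these SDs, the t test rejected a true null in 4.5%, 4.8%, 5.4% and 5.1% of trials for 4, 6, 10 and 20 raters. A separate set of runs (3, 6 or 15 raters, 10% to 50% of variance between raters) gave 4.5–5.4% for the t test and 4.5–5.6% for Mann–Whitney. With arms balanced within rater, the t test in those runs was conservative (1.1–4.6%).

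**Step 2: device preference varies, and the target is clinicians in general.** The average device effect is zero and arms are balanced within rater:

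- True SE = √(1.5 + τ²/K).
- False-positive rate ≈ 2 × [1 − Φ(1.96 × 1.388 / true SE)].
- Example, τ = 5 and K = 4: true SE = √(1.5 + 6.25) = 2.78; 2.72/2.78 = 0.98; rate ≈ 33%.
- Example, τ = 5 and K = 10: true SE = √(1.5 + 2.5) = 2.00; 2.72/2.00 = 1.36; rate ≈ 17%.

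| Raters (K) | τ = 5 | τ = 3 |
|---|---|---|
| 4 | 33% | 16% |
| 6 | 25% | 12% |
| 10 | 17% | 8% |
| 20 | 10% | 5% |

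Simulation with the same assumptions agreed: 34%, 26%, 17% and 11% for τ = 5, and 16%, 12%, 9% and 5% for τ = 3. Unstratified allocation, closer to Section 6 as written, gave slightly higher rates: 34%, 28%, 19% and 13%, and 20%, 15%, 10% and 7%.

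**Step 3: what each remedy does.** In the separate runs with varying device preference, the planned t test rejected in 6–46% of null trials. A clinician main effect alone did not repair this (5–49%); a t test on the per-clinician differences did (4–6%). A clinician factor therefore recovers precision for these clinicians, and only the per-clinician analysis supports a claim about others.

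**The case against.** The strongest reply is that the randomized unit is the patient. Clinicians are crossed with arm rather than nested in it, so the usual inflation of a cluster-randomized trial does not arise. This stands. A reader might infer that the planned p-values and intervals are simply wrong because ratings from one clinician are correlated. The documents do not support that: with differences in level only, and no stated stratification by clinician, the planned SE is the correct one for the unadjusted estimate. Adding clinician is then a gain in efficiency, not the repair of an error.

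A reader might also infer that the effective sample is the number of clinicians. That depends on unknown inputs. At τ = 3 with 20 raters, the rater part of the variance is 9/20 = 0.45 against 1.5 from patients; at τ = 5 with 4 raters, it is 25/4 = 6.25 against 1.5.

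Three further points stand. The documents make no claim about clinicians beyond this center and give no figure for varying device preference. Repeated rating is an inference, and a single study rater would fit the text equally well. The Hodges–Lehmann interval may not be intended for this outcome.

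A random-slope mixed model as the main analysis is also debatable. With few raters the slope variance is poorly estimated, and the model assumes normal errors for a bounded score for which the plan allows a rank test.

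What the objection does not remove is that the rater is undefined, that a factor likely to explain variation is left out, and that nothing limits how the result may be read.

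**Conclusion.** The point holds as a minor one. Section 9 ignores the rater for an outcome that clinicians supply, very probably many times each. If clinicians differ only in level, the planned comparison is valid at about 5% and loses roughly 11 percentage points of power (71% against 82%) under the assumed SDs of 15 and 8. It is too optimistic only when two conditions hold together: device preference varies between clinicians, and the result is read as applying to clinicians in general. The first is plausible for an unblinded rating, but its size is unknown, so the 5% to 33% in the table is a range of scenarios and not an estimate for this trial. The primary outcome, hypoxemia, is not touched.

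**What to change.** In Section 9, take clinician satisfaction out of the general rule for continuous variables and state the following:

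- Define who rates. If both the endoscopist and the anesthesia provider scored sessions, analyse the two separately.
- Compare arms with clinician as a factor, using the clinician code from the procedure record.
- Report the number of raters, the ratings per rater, and the arm difference for each clinician.
- Limit the conclusion to the participating clinicians, unless an analysis of per-clinician differences (or a clinician-by-arm term) supports a wider one.
- If rater identity cannot be recovered, keep the planned comparison, and state that it does not account for rater and does not generalize beyond these clinicians.

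Enrollment is complete, but the change is analytic and needs no new patient data. Because it comes after completion, the amended text should be dated and labeled as such. The cost is retrieving a clinician code and a short change of wording. The downside is that any claim about clinicians in general will have a wider interval, and with very few raters it may not be supportable.

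### The PSI analyses have no rule placing PSI before the hypoxemia event, so any PSI–hypoxemia association they give may partly reflect reverse causation

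*Combined protocol and SAP*

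**What the plan says.** Section 8.1 defines the primary outcome as "Incidence of hypoxemia during the procedure, defined as any occurrence of" SpO2 at or below 90%. The outcome window is therefore the whole procedure, including the first five minutes.

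Section 9 then sets out the analyses that bear on PSI:

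- The exposure: "PSI was defined as the mean between 5 and 20 minutes after induction".
- Directly after it: "Exploratory minute based logistic regression at 5, 10, 15, and 20 minutes used Bonferroni correction", with the threshold at 0.0125. Neither predictor nor outcome is named.
- "Multivariable logistic regression was used to identify predictors of hypoxemia". No covariates are listed.
- "Spearman correlation was used for associations between continuous variables". The pairs are not named.
- The analysis set for everything: "All analyses were performed in the intention-to-treat population".

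Section 7.2 adds that "Sedation was titrated to maintain SedLine PSI values between 50 and 80". No section gives the timing of hypoxemic events, what was done to sedation after one, how often PSI was recorded, or how long procedures lasted.

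**The concern.** An exposure should be measured before the outcome it is meant to explain. Here a patient who first desaturates at minute 3 contributes a PSI 5–20 value taken entirely after the event, and one who desaturates at minute 12 contributes a value taken partly after it. The same holds at each single minute: for anyone already hypoxemic by minute 10, the minute-10, 15 and 20 readings all follow the event.

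PSI was steered by titration, so it is not a fixed patient characteristic. If a desaturation leads to a change in sedation depth, later PSI is partly a consequence of the outcome. A model of any-time hypoxemia on that PSI mixes the effect of depth on hypoxemia with the effect of hypoxemia on depth. The trial's short title presents it as SedLine-guided, so readers may take a PSI–hypoxemia association as evidence about sedation depth.

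Two further points follow. PSI 5–20 is measured after randomization, so a model that includes it no longer gives a clean arm effect. And a patient whose procedure ended before minute 15 or 20 has no intra-procedure PSI at that minute, so a model at that minute cannot include every randomized patient.

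**Working it through.** **The plan's own figure.** Four tests at a two-sided 0.05: 0.05 / 4 = 0.0125, which reproduces the stated threshold. For four independent tests the family-wise error is 1 − (1 − 0.0125)^4 = 4.9%, against 1 − 0.95^4 = 18.5% uncorrected. This controls multiplicity only. It does not address an exposure measured after the outcome.

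**Inputs for the illustration.** From the documents: n = 600, the PSI window of minutes 5–20, hypoxemia at any time, and the 0.0125 threshold. Assumed, because the documents give no values: PSI SD 8; true odds ratio (OR) 1.0 or 0.70 per 10 points; a share s of first events preceding the PSI measurement; a rise of r points in PSI after an event. A fall would push the bias the other way.

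**Closed form.** With PSI roughly normal and equally variable in patients with and without hypoxemia, the log OR per 10 points is 10 × (difference in means) / SD². A post-event rise shifts the mean among hypoxemic patients by s × r, so

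ln OR(observed) ≈ ln OR(true) + 10 × s × r / 64, with ln 0.70 = −0.357.

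| s | r | 10·s·r/64 | OR if truth is 1.0 | OR if truth is 0.70 |
|---|---|---|---|---|
| any | 0 | 0 | 1.00 | 0.70 |
| 30% | 3 | 0.141 | 1.15 | 0.81 |
| 30% | 5 | 0.234 | 1.26 | 0.88 |
| 60% | 3 | 0.281 | 1.32 | 0.93 |
| 60% | 5 | 0.469 | 1.60 | 1.12 |

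Simulation of the 60% rows (400 replicates, 15% incidence) gave 0.93 to 1.11, in agreement. Reversal at s = 60% needs r > 0.357 × 64 / (10 × 0.6) = 3.8 points. At s = 30% it needs twice that, 7.6 points.

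**False positives with no true PSI effect, tested at 0.0125, rise of 3–5 points (simulated).** With 60% of events early: 19–56% at 10% incidence and 40–88% at 20% incidence. With 30% early: 5–26%. With no post-event rise the rate stays near nominal.

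**A second simulation that follows the 5–20 minute average.** Assumptions: 20% incidence, PSI mean 65, between-patient SD 8, minute-to-minute SD 3, 25–75% of first events before minute 5 and the rest uniform over minutes 5–25, 400 replicates per scenario.

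- No post-event change: OR 1.00–1.01 when the truth is 1.0, and 0.70 when it is 0.70. Overlap alone creates no bias.
- Rise of 3 points: 1.30–1.47 when the truth is 1.0 (p < 0.05 in 55–86% of replicates); 0.89–1.04 when it is 0.70.
- Rise of 5 points: 1.50–1.93 and 1.07–1.37 respectively.
- PSI taken before the event: about 1.0 and about 0.73, the latter slightly attenuated by measurement noise.

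These biases exceed the closed-form ones at similar early shares because patients who desaturate inside the window also contribute some post-event minutes, on average 37.5% of the window. With 25% early, the effective share is 0.25 + 0.75 × 0.375 = 0.53.

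**Availability at minute 20.** No durations are given. If procedure time were lognormal with log-SD 0.35, the proportion finished by minute 20 would be 50%, 26% or 12% for medians of 20, 25 or 30 minutes.

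**The case against.** The strongest reply is that much of the criticised model is inferred. Section 9 does not say that PSI is the predictor in the minute-based regressions, that any-time hypoxemia is their outcome, or that PSI enters the multivariable model. A minute-t model could already use hypoxemia after t, which would remove most of the problem. This stands, and it is why the point is conditional. It does not dispose of it: the regressions directly follow the PSI definition, PSI is the only variable Section 9 defines by minutes from induction, and no ordering rule is stated.

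Second, overlap of the windows does not bias anything by itself; a shift in PSI after the event is needed. That also stands. Titration makes a shift possible, but the documents state neither its size nor its direction.

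Third, the minute-based models are labelled exploratory, and PSI is neither an objective nor a listed outcome. This limits the severity.

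A reader might go further and infer that a PSI effect reported by this trial is spurious or reversed, or that the arm comparison is contaminated. The documents support neither. They report no PSI estimate. Reversal occurs only in the more extreme assumed scenarios. The arms are compared by chi-square or Fisher's exact test with relative risk and odds ratio, without PSI, and the multivariable model's stated purpose is to identify predictors. Nor do the documents show how many patients lack a PSI reading at minute 20; the 12–50% range comes wholly from assumed durations.

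**Conclusion.** The point holds in a conditional form, at moderate severity. The exposure window and the outcome window overlap, and no rule places PSI before the event. If the PSI models regress any-time hypoxemia on PSI 5–20 or on PSI at a given minute, part of the exposure follows the outcome for patients who desaturate early. If sedation depth also changes after a desaturation, the association is biased.

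The size cannot be fixed from the documents. It ranges from nil to attenuation to a null or reversed association, depending on the share of early events and the post-event change in PSI, neither of which is given. The 0.0125 threshold does not help in any of these cases. The randomized primary comparison and the between-arm comparisons of secondary outcomes do not depend on PSI and are unaffected, so this is not a defect that must be cured before the main result can be read.

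**What to change.** 1. Name the predictor and outcome of each minute-based model. At minute t, include only patients still in the procedure who have had no SpO2 at or below 90% by t, model hypoxemia after t, and report the number at risk and the number of events.
2. Do not relate PSI 5–20 to any-time hypoxemia. Use PSI recorded before the first event. A time-updated model is an option only if time-stamped PSI and SpO2 are held, which the documents do not say. If event times are not held, report the association as non-causal and possibly affected by reverse causation.
3. List the covariates of the multivariable model, and keep PSI 5–20 out of any model from which the arm effect is read.
4. Do not label the PSI models intention-to-treat. State how procedures that end before minute t are handled.

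The cost is revised wording and, where event times exist, a re-run of exploratory models. The trial is complete, so the re-run should be labelled post hoc. The statistical price is fewer events and wider intervals at the later landmarks.
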